## SUPPORTING MATERIALS

Below are summaries of trial results that present both mycological and clinical evidence to support the anticipated efficacy of the Erchonia® LunulaLaser™ for the treatment of onychomycosis, to be demonstrated in this current clinical study as the presence of complete clear nail with simultaneous negative mycological testing following treatment administration with the Erchonia® LunulaLaser™.

➤ **AN EVALUATION OF THE EFFECT OF THE ERCHONIA LUNULA™ ON TREATING TOENAIL ONYCHOMYCOSIS CLINICAL STUDY; Version 7.0; December 27, 2012; Erchonia Corporation: Mycology Results**

This study was pre-established as a positive mycology study such that as a condition of study enrollment, all subjects were required to have a positive mycology for onychomycosis as confirmed through toenail cultures taken during study qualification evaluation and sent to an independent laboratory to be grown in an agar solution used to clinically identify dermatophites that are consistent with a definitive and verifiable diagnosis of the presence of onychomycosis.

The mycology testing was performed at Lawrence Laboratories in Dublin, Ireland. It was established, registered and certified as a Manufacturer of pharmaceutical preparations on August 21, 1972 (Registration #38315), and was dissolved on December 16, 2013.

The methodology used for the mycology testing was the following:

- Core samples were obtained from under the nail plate as close as possible to viable tissue
- Cultures were then grown in a neutral dermatophyte medium (peptone-glucose agar solution) with cycloheximide
- The presence of verifiable dermatophites was confirmed by the agar solution turning a pink color. The presence of verifiable dermatophites is considered consistent with the condition known as onychomycosis.
- The samples were monitored for up to 21 days, with evaluations recorded on Days 3, 7, 14 and 21, as applicable.

In all instances of enrolled toenails, the presence of dermatophites was confirmed by the agar solution turning a pink color. Furthermore, the onychomycosis strain of *Trichophyton rubrum* (*T. rubrum*) was present on almost all slides. *T. rubrum* is established as the most common cause of onychomycosis in Europe and North America.

Mycology testing was repeated for all enrolled subject toenails at 2 weeks post baseline evaluation. The results demonstrated the conversion from positive mycology to negative mycology as a result of the treatment administration with the Erchonia® LunulaLaser™ for all enrolled and treated study subject toenails.

Specifically, mycology testing results were as follows:

- *Baseline (Pre-Treatment) Evaluation:* Baseline results for all study toenails was a positive mycology for onychomycosis, denoted by detection of the presence of verifiable dermatophites consistent with onychomycosis. The culture results also indicated the positive presence of the *Trichophyton rubrum* strain for all samples. *Trichophyton rubrum* is the most common cause of onychomycosis in North America and Europe. The presence of

dermatophites was detected by day 3 or day 7, and the species identified as *T. rubrum* by day 7 or 14 in most cases, at which time the sample was destroyed.

- **Two Weeks Post-Baseline Evaluation:** All samples were found to have a negative mycology, consistent with the absence of onychomycosis. There was no change seen across all evaluation points, and the sample was destroyed following Day 21 evaluation.

The results summary of the culminating trial that resulted in the FDA's clearance for K153164 for the Erchonia® LunulaLaser™ is provided below:

➤ **A RETROSPECTIVE EVALUATION OF THE EFFECT OF THE ERCHONIA LUNULALASER™ ON THE INCREASE OF CLEAR NAIL IN PATIENTS WITH TOENAIL ONYCHOMYCOsis; Version 1.0; September 29, 2015**

**BACKGROUND:** The purpose of this study was to demonstrate through retrospective analysis the efficacy of the Erchonia LunulaLaser™, manufactured by Erchonia Corporation, for the increase of clear nail in patients with toenail onychomycosis, when applying the LunulaLaser™ to the toenail for 12 minutes one time per week for a total of 4 procedure administrations.

**STUDY DESIGN:** This study was a retrospective analysis of a compilation of pre-procedure and six-month post-procedure photographs of fifty-four (54) great toenails with varying degrees of onychomycosis disease involvement selected from amongst an existing pool of photographs taken during three prior Erchonia Corporation research studies wherein 4 sequential weekly 12-minute procedures with the LunulaLaser™ were administered. The evaluating investigator was blinded to corresponding pre- and post-procedure photographs through application of a randomized numeric coding methodology.

**STUDY MEASURES:** The linear measurement of millimeter (mm) of clear nail from the proximal nail fold to the most proximal area of nail dystrophy was objectively measured from unmarked digital photographic images using the validated GNU Image Manipulation Program (GIMP 2.8) software system, a multi-platform image/photo manipulation software system, at baseline evaluation (prior to LunulaLaser™ procedure administration) and at 6 months following completion of the LunulaLaser™ procedure administration protocol.

**STUDY PROCEDURE:** Study great toenails had received 4 procedure administrations with the Erchonia LunulaLaser™ across a consecutive 3-week period: each procedure administration 7 days apart. Exposure time to the laser was 12 minutes, directed at and about 4 inches above the great toenail.

**SUBJECTS AND SAMPLE:** Fifty-four (54) treated great toenails of varying degrees of onychomycosis involvement at study entry were evaluated in this study. Subjects were 18 years or older with current bacterial/fungal infection classified by the investigator and confirmed through lab testing as positive for onychomycosis.

## STUDY RESULTS

**Primary Outcome Measure: Change in mm of Clear Nail from Baseline to Study Endpoint:** The primary efficacy outcome measure in this study was the mm of clear nail growth at 6 months post procedure administration end relative to Baseline (pre-procedure administration). Individual toenail success was defined as 3 mm or more of clear nail growth at 6 months post-

procedure end relative to baseline. Overall study success was defined as an anticipated 60% of treated toenails meeting the individual toenail success criteria.

Sixty seven per cent (67%) of all study treated toenails evaluated in this study met the study individual toenail success criteria, exceeding the pre-established overall study success goal of 60% by 7%. The magnitude of the mean change in mm of clear nail from baseline to 6 months post-procedure for all treated toenails was an increase of 5.18 mm, 2.18 mm in excess of the pre-established 3 mm increase success criteria. A t-test for paired samples found this mean change of +5.18 mm in clear nail to be statistically significant ( $t=-8.0$ ;  $df=53$ ;  $p<0.0001$ ).

**ADVERSE EVENTS:** No adverse event was reported or observed for any subject throughout any of the three clinical trials from which this study's retrospective sample was drawn.

**CONCLUSION:** The Erchonia LunulaLaser™ is an effective tool for increasing clear nail in toenails infected with onychomycosis, significantly increasing mm of clear nail over a 6 month period following completion of the 4-week procedure administration phase.

## **STUDY DESIGN**

### **STUDY TREATMENT GROUP**

There will be an active test treatment group only in this study such that all study subjects will receive the active laser treatments with the Erchonia® LunulaLaser™. The absence of a control group was stipulated by FDA through prior Pre-IDE reviews and was subsequently established and accepted through the Erchonia® LunulaLaser™ Retrospective Analysis Study whose results successfully supported clearance of the Erchonia® LunulaLaser™ for the increase in clear nail in patients with toenail onychomycosis, under K153164.

### **BLINDING DESIGN**

Given that there is only an active treatment group in this study, there is no need for blinding of either the subject or the study investigator administering the study treatments with the Erchonia LUNULA™ device. All subjects and investigators will be aware that the study treatment being administered will be the true active laser treatment.

### **RANDOMIZATION**

Given that there is only an active treatment group in this study; randomization to treatment group is not applicable.

### **SUBJECTS**

#### Recruitment

The recruitment process will work as follows:

1. An individual voluntarily schedules an appointment at the physician's office (that in the context of this clinical study also functions as the investigator's test site) regarding his or her toenail fungus.
2. Through this visit, if the physician perceives that the patient may satisfy the study qualification criteria (i.e. there are no obvious indicators that may exclude him or her), then the physician will present the option of being a subject in the study.
3. If the patient is interested in possibly taking part in the study, the physician – now in the role of study investigator – will personally review the informed consent form with the individual and answer any questions. The individual may sign the informed consent form at that visit or he or she may think about it for a while and sign the informed consent form at a later time (taking as long as desired, from hours to days, to sign as long as study enrollment is continuing at the time the decision to sign is made) or he or she may refuse to participate.
4. An individual who chooses to sign the informed consent form and proceed with study participation will receive a subject ID and proceed to the study qualification evaluation phase.
5. An individual who decides not to participate in the study will continue to work with the physician to determine a treatment plan for his or her toenail onychomycosis.

#### Compensation

A subject will not be offered money or any other form of compensation to participate in the clinical study. However, he or she will also not be charged for the cost of the study treatments with the Erchonia® LunulaLaser™, the cost of the mycological lab testing or for the cost of any other directly-related evaluations or measurements that occur as part of his or her participation in the study.

Sample size

There will be 66 qualified subjects/great toenails enrolled in this clinical study across three test sites, approximately 22 subjects/great toenails per test site.

Rationale for sample size

The sample size of 66 subjects/great toenails was calculated based upon the 95% one-sided confidence interval (i.e. lower bound only) around the observed response rate of 70% being  $\geq$  50% (56%) yielding a pre-determined final sample size of 60 subjects/great toenails. From here, it is anticipated that about one-twelfth of subjects overall may withdraw or be terminated from the study prior to completion for various reasons. Therefore, the following formula is used to determine the final needed starting sample size for each procedure arm:

Final sample size = sample size  $\times$   $1/(1-d)$ ; where  $d$  = # expected dropouts/# subjects enrolled

Final sample size =  $60 \times 1/(1-0.082)$

Final sample size =  $60 \times 1/0.917 = 60 \times 1.091 = 66$  subjects

Therefore, a minimum starting sample size of 66 subjects is needed to insure that a sufficient number remains at the end of the treatment administration phase (60 subjects), assuming a drop-out rate of around one-twelfth, for a positive study outcome to be considered statistically valid, clinically meaningful and representative of the general population being sampled.

Subject Recruitment Advertisement

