### **PRIMARY EFFICACY OUTCOME EVALUATION**

The primary efficacy outcome measure in this study is the Complete Cure Rate at study endpoint.

Individual Subject Success Criteria: 'Complete Cure' criteria is defined as a subject/toenail satisfying both the 'Clinical Cure' and the 'Mycological Cure' criteria in order to be considered a study responder, defined as follows:

(i) Clinical Cure: Measurement of clear nail increase as the following:

- at least 12 mm increase in clear nail of the great toenail, with evidence of distal growth of the affected area, 12 months after the first treatment;  
or
- complete clearance 12 months after the first treatment if less than 12 mm distal nail was involved prior to treatment.

The response should be progressive in at least 2 sequential timepoints that are at least 3 months apart, with projected increase of at least 1 mm per month.

(ii) Mycologic Cure: Negative Fungal Culture results

Overall Study Success Criteria is defined as both of:

(i) a minimum 70% Clinical Cure Clear Nail Responder Rate;

AND

(ii) Among toenails which are deemed responders based on the Clinical Cure Clear Nail criteria, at least 80% will also demonstrate Mycological Cure.

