## **PRIMARY EFFICACY OUTCOME STATISTICAL EVALUATION METHODS**

- **Intent to Treat (ITT) Principle:** Primary efficacy analysis will be according to the intent to treat (ITT) principle; wherein subjects will be included in the analysis if they had a valid Baseline Assessment visit.
- **Missing data** will be handled through *Last Observation Carried Forward (LOCF)*: by carrying forward the last recorded observation to fill in the subsequent missing value.

Subjects who drop out or are lost to follow-up will be considered as treatment failures (non-responders) in the statistical evaluation.

- **Per-Protocol Analysis** will also be performed for the set of all subjects who completed the study according to the full protocol.
- **Primary analysis of efficacy** according to *intent to treat* (ITT) analysis will be through determination of satisfaction of the Overall Study Success Criteria.

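### The sample size is justified on 60 completers, but the primary rule counts dropouts as failures among all 66, so an observed 70% of completers (42/60) becomes 63.6% and fails; the 60 also does not follow from its stated inputs

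*Combined protocol and SAP*

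**What the plan says.** **Sample size** (Study Design, Rationale for sample size). The number comes from a "95% one-sided confidence interval (i.e. lower bound only" that is placed "around the observed response rate of 70" per cent. The bound is to be at least "50% (56%) yielding a pre-determined final sample size of 60 subjects/great toenails". On dropout, "it is anticipated that about one-twelfth of subjects overall may withdraw or be terminated from the study prior to completion". The 60 is therefore inflated to 66, in order to "insure that a sufficient number remains at the end of the treatment administration phase (60 subjects").

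**Success rule** (SAP, Primary Efficacy Outcome Evaluation). Criterion (i) is "a minimum 70% Clinical Cure Clear Nail Responder Rate". Criterion (ii) asks that at least 80% of those clinical responders also have mycological cure. Both are rules on the observed percentage.

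**Analysis set and dropouts** (SAP, Primary Efficacy Outcome Statistical Evaluation Methods). In the primary ITT analysis, "subjects will be included in the analysis if they had a valid Baseline Assessment visit". Further, "Subjects who drop out or are lost to follow-up will be considered as treatment failures (non-responders) in the statistical evaluation". The primary analysis consists of checking whether the overall success criteria are met; no confidence bound enters the decision. The same section also names LOCF for missing data and adds a per-protocol analysis of completers.

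**The concern.** Inflating a sample size for dropout makes sense when dropouts leave the analysis. Here they stay in the denominator and count against the device. The rationale therefore describes precision among 60 completers, while the trial is judged by a percentage of all 66.

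The rationale ties its 60 remaining subjects to a positive outcome being valid, so a reader would take an observed 70% among those 60 as a success. Under the SAP it is a failure. This is a single-arm trial and the rule is its only primary efficacy decision. Yet the plan gives no assumed true rate and no probability of meeting the rule, so nobody can judge from it whether 66 is adequate.

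The derivation of 60 raises a second, smaller question: do the stated confidence level, response rate and target bound lead to that number?

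**Working it through.** **Inputs.** From the sample-size rationale: one-sided 95% bound, observed rate 70%, target bound 50% (56% in brackets), n = 60, dropout one-twelfth, 66 enrolled. From the SAP: thresholds of 70% and 80%, all subjects with a valid baseline analysed, dropouts as non-responders. I assume that all 66 have a valid baseline visit and that 66 − 60 = 6 are lost.

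**1. The plan's own figures.** The step from 60 to 66 reproduces: 60/(11/12) = 65.45 and 60/0.917 = 65.43, both rounded up to 66. The inputs are not quite consistent, since one-twelfth is 0.083, the formula shows 0.082, and 1 − 0.082 is 0.918 rather than 0.917. None of this changes 66.

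The 60 does not reproduce. The one-sided 95% lower bound for 42/60 is:

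- Wald: 0.70 − 1.645 × √(0.70 × 0.30/60) = 60.3%
- Wilson: 59.6%
- exact (Clopper–Pearson): 58.8%

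None is 56%. Working backwards, the smallest n with a bound of at least 50% is 15 to 22, and with at least 56% it is 29 to 41, depending on the interval method. With whole responders at exactly 70%, the exact bound is 53.5% at 21/30, 56.0% (just under 56) at 28/40 and 57.6% at 35/50.

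**2. The success rule on the analysed denominator.** 0.70 × 66 = 46.2, so 47 responders are needed (46/66 = 69.7% fails; 47/66 = 71.2% passes). With 6 lost, 42/60 becomes 42/66 = 63.6%. With 5 lost, 70% of 61 is 42.7, and 42.7/66 = 64.7%, which also fails. The completer rate needed is 47/(66 − d) for d dropouts:

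| Lost | 0 | 1 | 3 | 6 | 8 |
|---|---|---|---|---|---|
| Completer rate needed | 71.2% | 72.3% | 74.6% | 78.3% | 81.0% |

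More enrolment would not help. At a 70% completer rate and one-twelfth dropout the expected ITT rate is 0.70 × 11/12 = 64.2% whatever the sample size.

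**3. Probability of meeting criterion (i).** The plan gives no true rate, so several are shown, with subjects taken as independent. The three columns are P(Bin(60, p) ≥ 47), P(Bin(66, 11p/12) ≥ 47) and P(Bin(66, p) ≥ 47).

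| Assumed true rate p | p among completers, exactly 6 lost | p among completers, random one-twelfth dropout | p already an ITT rate |
|---|---|---|---|
| 70% | 10% | 14% | 47.5% |
| 75% | 33% | 39% | 80.5% |
| 80% | 69% | 71% | 97% |
| 85% | 94% | 92% | >99% |

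For comparison, P(Bin(60, 0.70) ≥ 42) = 56%, the chance if only the 60 completers counted. For a 50, 80 or 90% chance with 6 lost, the true completer rate must be about 77, 82 or 84%. As an ITT rate it must be 70, 75 or 77%.

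**4. Probability of meeting both criteria.** Sum over k ≥ 47 of P(k clinical responders) × P(Bin(k, m) ≥ 0.8k), where m is the mycological cure rate among clinical responders.

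| Clinical cure rate | m = 80% | 85% | 90% | 95% |
|---|---|---|---|---|
| 70% of completers, 6 lost | 5% | 8% | 10% | 10% |
| 75% of completers, 6 lost | 17% | 28% | 33% | 33% |
| 80% of completers, 6 lost | 36% | 59% | 68% | 69% |
| 85% of completers, 6 lost | 50% | 80% | 93% | 94% |
| 70% ITT | 25% | 40% | 47% | 47% |
| 75% ITT | 42% | 68% | 79% | 80% |

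**The case against.** The best defence is that the rationale is only a precision statement: at the minimum passing rate, the lower bound clears 50%. That is true on either denominator (exact bound 58.8% for 42/60 and 60.7% for 47/66), and even the failing 42/66 has a bound of 52.8%. The text never calls 70% a completer rate, and 60 completers would suit the per-protocol analysis. This shows that 66 is not too small for a bound above 50%, and that point stands. It does not rescue the rationale, because no bound decides the trial, the per-protocol set is not primary, and retaining 60 is given as the reason for enrolling 66.

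LOCF, named in the same SAP section, might seem to soften the dropout rule. The sentence treating dropouts as failures is explicit and more specific. Even under LOCF, 42 completer responders would need 5 of the 6 dropouts carried forward as responders to reach 47.

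The bracketed 56% may be the exact two-sided 95% lower bound for 42/60, which is 56.8%; but the plan says one-sided, so that would be an error of sidedness. It also equals 70% × 80%, the product of the two criteria. The documents support neither reading.

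Finally, the low probabilities depend on the assumed rate. At a true ITT rate of 80%, criterion (i) is met 97% of the time. That is why ranges are given and no single figure is put forward as the expected result.

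**Conclusion.** The concern holds, and should be fixed. The sample-size rationale and the primary decision rule use different denominators and different criteria, and the 70% on which the rationale rests fails the rule once 5 or 6 subjects are lost. With 6 lost, the hurdle among completers is 78.3%. If the true completer rate were 70%, counting dropouts as failures would cut the chance of meeting criterion (i) from 56% to 10%. This rests on all 66 having a valid baseline, on the sponsor's own dropout figure, and on reading the 70% as a rate among those remaining. If it is an ITT rate, the chance is 47.5%.

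That 60 cannot be derived from the stated inputs is a lesser fault. It errs on the safe side for a bound of 50%, and the step from 60 to 66 is sound.

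**What to change.** Keep 66 subjects and the success rule. Replace the rationale with text along these lines:

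> All enrolled subjects with a valid Baseline Assessment (planned 66) are analysed, and those who drop out count as non-responders. Criterion (i) requires at least 47 of 66 clinical responders, which is 47 of 60 completers if 6 are lost. The assumed true clinical cure rate is [sponsor to state]% among [completers / all enrolled]; the assumed mycological cure rate among clinical responders is [sponsor to state]%. The probabilities of meeting criterion (i), and both criteria, are tabulated over a range of these rates. For description only: 42/60 has an exact one-sided 95% lower bound of 58.8%; with 6 dropouts the result is 42/66 = 63.6%, lower bound 52.8%, which does not meet criterion (i).

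Attach the ranges above as the table. Say what the 56% means or delete it, and use one dropout figure throughout. In the SAP section on primary statistical methods, add one sentence:

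> For the responder endpoint, subjects who drop out are non-responders; LOCF does not override this.

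The cost is one paragraph, a small table and one sentence. No subjects are added, and the rule and the analysis are unchanged. The sponsor must commit to assumed rates, and the stated chances of success will look less favourable than the present text suggests.

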## Toenail Fungus Research Study

This study is to see if the Erchonia LunulaLaser™, a non-invasive device that uses low-level laser light to grow new nail in toenails with toenail fungus can help to get rid of the fungus in the toenail altogether.

The study involves 12 visits to a test site over about 14 months.

Please contact  
<Test Site/PI name> at <phone#> or  
<e-mail> for details.

## **STUDY PROCEDURE**

### **STUDY TEST BATTERY**

The following assessment tools will be used in this study. For each study phase, the precise tool that will be employed will be specified.

## **BASELINE VARIABLES**

### **BASELINE TARGET TOENAIL VARIABLES**

- (i) Location of target toenail: right foot; left foot.
- (ii) Duration of onychomycosis in target toenail: months/years since observed onset
- (iii) Notation of any other toenail(s) on the target foot that appear to be infected with onychomycosis.

